Patients in the OCA mesh cohort will be compared to patients who have a closure with a running monocryl suture and dermabond. This investigation seeks to determine if OCA closure mesh closure is non-inferior to monocryl suture and dermabond in terms of operative time, cost, complications, and aesthetic appearance.

If the hypothesis is confirmed, this study will suggest that a OCA mesh closure may be used for total shoulder arthroplasty surgeries as an alternative to current conventional closures and may provide a cost benefit.

Specific Goal:

1) To specifically be able to make a recommendation of total shoulder wound closure based on complications, aesthetic result, time to closure, and cost

Specific Aims:

- 1) To compare the timing of total shoulder closure between OCA mesh and monocryl/dermabond closure
- 2) To compare the costs of the OCA mesh closure versus monocryl/dermabond
- 3) To compare the complications the OCA mesh closure versus monocryl/dermabond closure
- 4) To compare the healing and patient satisfaction of wounds between the OCA mesh closure versus monocryl/dermabond closure

Study Plan:

The study will be implemented at the Wakefield Campus of Montefiore medical center by randomizing patients undergoing total shoulder arthroplasty to receiving closure with monocryl and dermabond versus dermabond with self-adhering mesh. Participants will be subsequently followed for 3 months to evaluate wound healing and monitor for complications.

Methods:

- Design Prospective randomized intervention
- Setting Wakefield Hospital of Montefiore Medical Center
- Participants Patients who agree to participate in the study undergoing total shoulder arthroplasty
- Study Period
 - \circ Sample size 22 patients
 - Determine using a standard between-groups sample size calculation with a type 1 error rate of 5% and 80% power to detect a moderate effect size (0.5 standard deviation)
 - o Inclusion
 - Total shoulder arthroplasty
 - Reverse total shoulder arthroplasty

- Age 18-100
- Single Surgeon
- o Exclusion
 - Previous shoulder surgery
 - Known wound healing complications
 - DM, chronic steroid use, vascular insufficiency, morbid obesity (BMI>40), ESRD, family hx of pathologic scars
 - Patients on blood thinners (ASA 81mg ok)
 - Connective tissue disease
 - Allergy to skin adhesive
 - Mentally unable to complete questionnaires
 - Previous wound over planned incision
- Measures
 - o Time for closure
 - Cost of closure (time in OR, materials)

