 - Wound cosmesis
 - Patient and Observer Scar Assessment Scale (POSAS)
 - Wound complications (i.e. dehiscence)
 - Wound drainage
 - Infection (superficial vs. deep)
 - Length of stay in hospital
- Endpoints
 - o Primary endpoint is to determine which method of closure is faster
 - Secondary endpoints will include cost of closure, difference in wound complications, aesthetic differences, and difference in patient satisfaction
- Independent Variables
 - o Age
 - o BMI
 - o Race
 - o Gender
 - Length of Incision
 - Depth of Incision
 - o Prealbumin
 - o Albumin
 - o Glucose
- Randomization and blinding
 - A random number generator will be used to assign patients to the study and control groups. Patients will not be notified which group they had been assigned to, though they may be able to determine which group they are in after looking at their wound.

Study Protocol:

20 total shoulder replacement patients presenting to Wakefield Medical Center will be screened for eligibility according to the inclusion and exclusion criteria by study personnel. Medical history and demographic data will be collected and assessed to ensure

that patients meet the inclusion and exclusion criteria. Eligible subjects will be enrolled after informed consent is obtained.

- Prospective Randomized Design
 - After determining a patients' eligibility for inclusion, they will be randomized to the OCA mesh group or monocryl with dermabond group. After surgery, both groups will be seen at their 2 week, 6 week, and 3 month appointment.
- Surveys
 - At the 6 week, and 3 month follow up appointment both groups and the same surgeon will complete a patient observer and scar assessment scale survey
 - The Patient Observer and Scar Assessment Scale validated instrument created to measure patients and physician overall satisfaction with surgical wound appearance / healing [17]
- Data Collection

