 - For each enrolled subject, we will collect data from hospital presentation to discharge on standard demographics, routine laboratory results, clinical information, past medical history and hospital course data (length of stay, mobilization status, associated inpatient procedures and complications). Major complications are defined as: all-cause re-hospitalization, re-hospitalization relating to index surgery, DVT, PE, deep wound infection, dislocation, fracture, death. Minor complications include: UTI, delayed wound healing, superficial wound infection. Complications resulting from the surgery will be distinguished from those resulting from pre-existing conditions and comorbid states.
 - All the data will be recorded and stored in a password-protected Excel spreadsheet on study personnel password-protected work computers.
- Statistical Considerations
 - o Power Analysis
 - Power Power analysis (IBM SPSS 21) was performed before the study at a level of 0.05 alpha error and 0.8 beta error. Looking at closure time of total shoulder arthroplasty wounds, looking for an effect size of 13 minutes between closure groups determined that a sample size of 2 patients in each group was adequate to detect significant differences in closure times between groups. Increasing group size to 5 patients in each group resulted in a power of 88% at an alpha of 0.05 and using 10 patients in each group resulted in 100% power at an alpha of 0.05.

Measures to address study aims:

To address specific aim 1: We will first measure the length of the incision and depth of the wound with a intraoperative flexible ruler prior to closure. We will assess the timing of closure in the operating room by the surgeon announcing the start of closure. At this time, the circulating nurse will start monitoring time with a stopwatch. Once the dressings are completely on, the surgeon will announce to end time and the circulating nurse will stop the stopwatch. The timing of closure will be recorded.

To address specific aim 2: We will compare the costs of the two closure methods by determining the cost of the medical supplies used for closure, as well as calculating the cost of the operating room time that was required for each closure. The sum of these costs will be the total cost of closure.

To address specific aim 3: We will compare complications, including drainage and infection, between the groups over a 3 month period.

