To address specific aim 4: We will compare POSAS scores between the study group and control group at the 6-week postoperative follow up visit and 3 month postoperative follow-up visit.

Informed Consent

Informed consent procedure will take place during the preoperative consultation in the clinic setting or at any point during the hospital admission where the procedure is to be performed. This consent process will occur prior to the day of surgery. Study personnel including [name], [name], or [name] will approach patients in a manner, time, and location that insure participant privacy. Information about the study will be conveyed to the participant in simple understandable English. The information that will be provided to prospective subjects will include the studies purpose, the risks associated with the study, the potential benefits of the study, study requirements, and a request for compliance with study procedures.

Ample time and opportunity for patients to consider all options and ask questions will be given before signing the informed consent form. All participants' questions will be answered. Verbal confirmation that the participant has comprehended the information and options provided will be obtained through Talk Back technique.

Upon agreeing to participate in the study, patients will provide written consent using an IRB-approved informed consent document. Enrolled subjects will be provided with copies of signed consent documents. Efforts will be made to continue to provide information and options as the participant or research requires.

Safety Considerations

Total joint arthroplasty closure techniques vary widely based on surgeon preference and practices. In shoulder arthroplasty, closure with monocryl suture, dermabond, nylon suture, and staples have all been used. In total joint arthroplasty, OCA mesh closure is also used. Safety risks of the OCA mesh may include wound dehiscence, drainage, infection and need for re-operation. However, these risks are minimal and should not be significantly different in the control and study groups. If there is any concern that the OCA mesh is leading to increased complications, the study will be abandoned. Additionally, if there are indications of wound complications that need alternative treatment, including revision closure, the study will be abandoned. Pregnancy testing will be done as part of the normal preoperative labs in women of child-bearing age.

Confidentiality of Research Records

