Confidentiality will be protected by assigning a unique masked ID that will be linked to subjects' identifiers (e.g., name).

Storing documents in hard copy:

Any documents that contain PHI (e.g., consent forms, link between the ID to subjects' identifiers, de-identified research documents) will be stored in a locked cabinet within the office of [name]. IRB-approved study personnel will be the only individuals with access to any research documents containing PHI.

Storing Documents Electronically

Any documents that contain PHI (e.g., consent forms, subject identifier/deidentifier table) will be stored in a password protected computer document on the primary investigator's desktop computer. Only IRB approved personnel will be the only individuals with access to any research documents containing PHI. Randomization information will be kept in a password-protected file on the computer of [name].

Storing Documents on Portable Electronic Devices

No PHI or research data will be stored on any portable electronic devices (e.g., laptops, tablets, flash drives, etc.)

Emailing Data

Any research data that will be emailed will be de-identified and encrypted according to Montefiore Medical Center ITS department standards. PHI will not be emailed to any commercial email addresses.

Potential Benefits

The proposed potential benefits of this study may include faster surgical times, decreased operative costs, equivalent or improved complication rates, and improved patient satisfaction. There is evidence to support OCA mesh closure is faster and has similar complications.

Follow-up procedures

The data collection period for each patient will begin during the preoperative visit and end after each patient completes the in clinic 3-month follow up visit and study surveys patient reported outcome scores will be followed indefinitely.

Early termination/discontinuation of the study protocol

Once enrolled, patients may elect to discontinue participation in the study at any time, as per the language set forth in the consent document. Note: if randomized and subjects opt out afterwards, they will be in the intention to treat category. Patients who elect to leave the study will not be followed further and their data will be managed in an appropriate fashion.

Data and Safety Monitoring

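### Patients who opt out stay in the intention-to-treat group but are not followed and have no missing-data rule, so any early leaver makes the 3-month complication and scar comparisons available-case

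*Combined protocol and SAP*

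**What the plan says.** The rule is in the section on early termination/discontinuation of the study protocol. It allows departure at any point: "Once enrolled, patients may elect to discontinue participation in the study at any time". It then gives the analysis status of those who leave after assignment: "if randomized and subjects opt out afterwards, they will be in the intention to treat category". The next sentence reads: "Patients who elect to leave the study will not be followed further and their data will be managed in an appropriate fashion". No analysis set, imputation, sensitivity analysis or dropout allowance is defined anywhere in the document.

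The outcomes exposed to this rule are the later ones. The Study Plan says: "Participants will be subsequently followed for 3 months to evaluate wound healing and monitor for complications". For aim 3 the plan is: "We will compare complications, including drainage and infection, between the groups over a 3 month period". For aim 4 it is: "We will compare POSAS scores between the study group and control group at the 6-week postoperative follow up visit", and again at 3 months.

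The primary outcome is different. Under Endpoints, "Primary endpoint is to determine which method of closure is faster", and the measures for aim 1 have it timed by stopwatch in the operating room. On assignment, the Study Protocol section says: "After determining a patients' eligibility for inclusion, they will be randomized to the OCA mesh group or monocryl with dermabond group". It gives no interval between assignment and surgery. The Informed Consent section places consent before the day of surgery.

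**The concern.** An intention-to-treat comparison needs either outcomes on everyone randomised or a stated way of dealing with those that are missing. For anyone who leaves, the plan rules out the first and does not supply the second. Followed as written, the intention-to-treat label would sit on analyses of whoever happened to stay.

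This matters for aims 3 and 4 because the hypothesis claims non-inferior complications and satisfaction for the mesh, and the specific goal is a recommendation that rests partly on complications and appearance. Loss need not be random. The blinding paragraph accepts that patients may work out their group on seeing the wound, so a decision to leave after surgery could depend on both the closure and how it looks. If patients with poor wounds leave one arm more often, that arm looks better than it is.

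A smaller gap concerns the primary outcome: a patient who opts out after assignment but before surgery contributes no closure time.

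**Working it through.** The plan states no figure on this point to reproduce, so the check compares its statements and then sizes the effect of a loss.

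**Availability of each outcome by time of leaving**

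| Patient leaves | Closure time | Complications to 3 months | POSAS, 6 weeks and 3 months |
|---|---|---|---|
| After assignment, before surgery | missing | missing | both missing |
| After surgery, before 6 weeks | present | incomplete | both missing |
| Between 6 weeks and 3 months | present | incomplete | 3-month score missing |

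In every row the patient remains in the intention-to-treat category, and no rule says how the empty cells are handled.

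**Arm size.** Methods gives 22 patients; the Study Protocol section gives 20 to be screened, and the power paragraph speaks of 10 per group. Assuming equal allocation, an arm has 22/2 = 11 or 20/2 = 10 patients. One loss is 1/11 = 9.1% or 1/10 = 10.0% of an arm.

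**Hypothetical distortion.** Suppose an arm of 11 truly has two wound complications: 2/11 = 18.2%. Suppose one of them occurs, unrecorded, in a patient who has left.
- Leaver kept in the denominator and counted as event-free: 1/11 = 9.1%.
- Leaver dropped: 1/10 = 10.0%.

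The two complications and the unseen event are assumptions made for illustration.

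**Best/worst-case bounds.** If no complications are observed and w patients per arm are lost, the risk difference is known only to within ± w/n.
- w = 1: ± 1/11 = 9.1 points, or ± 1/10 = 10 points.
- w = 2: ± 2/11 = 18.2 points, or ± 2/10 = 20 points.

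**Chance that the issue arises.** No withdrawal rate is given, so a range is assumed. P(at least one withdrawal) = 1 − (1 − d)^N.

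| Assumed d | N = 22 | N = 20 |
|---|---|---|
| 5% | 68% | 64% |
| 10% | 90% | 88% |
| 20% | 99% | 99% |

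These count withdrawal at any time. Those that occur after the 3-month visit would do no harm.

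**The case against.** A reader might infer that the two adjacent sentences contradict each other and make an intention-to-treat analysis impossible. The documents do not support that. Ending follow-up when someone leaves is an ordinary withdrawal rule, and keeping that person in the assigned arm creates a missing-data problem that a pre-specified method could handle. Opting out and leaving the study might even be meant as two different situations; the text does not settle it. What stands is that no method is given.

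A reader might also infer that the consent form offers no partial withdrawal. That cannot be asserted: the section defers to the consent document, which is not available here. Nor does the plan say that data collected before withdrawal are discarded.

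The pre-surgery gap is also easy to overstate. Assignment is said only to come after eligibility, with no timing, and patients are not told their group. A patient who leaves before surgery should therefore have little reason to do so because of the arm, so the loss costs information more than it creates bias.

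On size, the 2/11 example is constructed. A patient unhappy with a wound may have had the problem recorded in the hospital data or at the 2-week visit before leaving. Under Safety Considerations, some wound complications would lead to the whole study being abandoned. Chance variation is also far larger than the shift: exact 95% intervals are about 2–52% for 2/11 and 0.3–45% for 1/10. All of this stands. It limits the point to a conditional weakness in the secondary outcomes.

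**Conclusion.** The point holds in a limited form. As written, the plan labels leavers intention to treat, stops observing them and gives no rule for what is then missing. If anyone leaves before 3 months, the aim 3 and aim 4 comparisons become available-case. Each loss is 9–10% of an arm, and one loss per arm leaves the complication risk difference uncertain by 9 to 10 points even if no events are seen.

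It would be wrong to read this as a threat to the primary comparison in general. Closure time is unaffected by withdrawal after surgery and is lost only if a patient opts out between assignment and closure. Nor do the documents show that either arm would be favoured. The sizes rest on equal allocation and on assumed withdrawal rates. This is a cheap improvement, not a major flaw.

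**What to change.** 1. **Study Protocol, Prospective Randomized Design:** make the random assignment in the operating room, after the incision is measured (already planned before closure) and before closure starts. This leaves practically no interval for opting out between assignment and the closure-time measurement.
2. **Early termination section:** replace the sentence that ends follow-up with a rule that data up to withdrawal are kept and analysed as randomised. For patients who stop study procedures but agree, complications are read from the routine 2-week, 6-week and 3-month clinic notes. This needs a consent option if the consent form does not already have one.
3. **Statistical Considerations:** report withdrawals by arm, and add a best/worst-case sensitivity analysis for complications missing after withdrawal. In the hypothetical above, setting the leaver's status each way gives 1/11 to 2/11 (9.1% to 18.2%), which contains the true value.

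Chart review cannot recover patient POSAS scores. These stay missing after withdrawal, and the aim 4 comparison should be reported as available-case.

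Cost: both closure kits ready at each case, some protocol sentences, possibly one consent option, and a short chart review. Some patients will decline the chart review, so the sensitivity analysis is still needed.
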